3.7 Randomisation Process

Patients will be randomised by the selection of sealed envelopes with one of the two approaches listed inside. There will have 86 envelopes, 43 containing the anterolateral approach and 43 containing the posterior approach. The envelopes will be generated in advanced by the research team and will be unidentifiable once sealed. They will be allocated at random to the 86 participants. The envelopes will be kept in a locked filing cabinet in the orthopaedic department and once opened, the contents will be filed in the patients notes.

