3.8 Informed Consent

Informed consent will be obtained during the initial clinic visit after the patient has had adequate time to read the information leaflet, digest the information provided and ask any questions they may have, as well as express their views/wishes. The patient will be asked to sign a consent form indicating they have understood all aspects of the study and their rights. This form will also be signed by the researcher and three copies of this form will be obtained (one for patient, one for researchers which will be stored in the study site file and one for the clinical notes).

Withdrawal of Subjects

Patient will be free to withdraw from the study at any time without explanation and without prejudice. A patient will be withdrawn from the study, if unable to tolerate the injection or does not comply with physiotherapy. Abrupt termination of patient from study will not put the patient at risk. The patient will still be offered care as they would be routinely, if unable to continue in study for whatever reason.

If patient fails to attend the follow up clinic visit then a letter will be sent to the patient and copied to the GP as is done routinely when a patient does not attend. A follow up appointment will then be booked for the nearest possible date.

4 Prior and Concomitant Therapy

There are no restrictions to prior or concomitant medicines permitted during the study.

The only therapy that patients will receive will be physiotherapy.

5 Laboratory Assays

Not applicable

6 Study Procedures

All relevant procedures are detailed above.

7 Statistical Plan

The study statistician has calculated the number of participants needed for the study, so that the study can reliably answer its aims, whilst avoiding wastage of time and resources. Statistical methods have been used for sample size calculation as follows: the standard deviation for change in Oxford Shoulder Score (OSS) at 12 weeks from baseline was obtained from a previous study of steroid injection for shoulder pain (Holt, TA et al[11]). 43 patients in each group are needed based on 80% power for a two sample t-test, detecting a minimal important difference of 6 and a two-tailed significance level of 0.05 with a standard deviation of 9.1. This accounts for 10% attrition between baseline and 3 months as documented in the previous study (Holt, TA et al[11]).

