Baseline demographic and clinical variables will be reported using summary statistics. In terms of the primary outcome, the change in total Oxford Shoulder Score from baseline to 3 months post-injection will be compared between the two groups using either the Independent Samples t-Test or Mann-Whitney U Test, with the final choice depending on an exploration of the data. The same approach will be adopted for secondary outcomes. All analysis will be performed according to the intention to treat principle.

8 Safety and Adverse Events

There is no deviation in normal practice with regards to the medication being given, therefore standard pharmacovigilance procedures will be used.

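### The primary test on change in OSS leaves out about 9 of 86 randomised patients under an intention-to-treat label and does not adjust for baseline OSS; a baseline-adjusted longitudinal model with a missing-data sensitivity analysis is better

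*Combined protocol and SAP*

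**What the plan says.** Section 7, with the same text in the Statistical Analysis row of the Study Summary, says that "the change in total Oxford Shoulder Score from baseline to 3 months post-injection will be compared between the two groups". Two candidate tests are named and the decision between them is left open: "using either the Independent Samples t-Test or Mann-Whitney U Test, with the final choice depending on an exploration of the data". It then states: "All analysis will be performed according to the intention to treat principle". It does not define the analysis set, gives no method for a missing 3-month score and has no sensitivity analysis.

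The sample size paragraph of section 7 says "43 patients in each group are needed based on 80% power for a two sample t-test". Its design values are given as "detecting a minimal important difference of 6 and a two-tailed significance level of 0.05 with a standard deviation of 9.1". On losses it adds: "This accounts for 10% attrition between baseline and 3 months as documented in the previous study". Section 3.7 fixes the total: "There will have 86 envelopes, 43 containing the anterolateral approach and 43 containing the posterior approach".

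Three other provisions bear on the point:

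- OSS is also collected by post at 6 months and 1 year (section 1.1, section 2 and section 3.1.2).
- The paragraph on withdrawal of subjects after section 3.8 takes a patient out of the study for not tolerating the injection or for not adhering to physiotherapy.
- The same paragraph says that a missed clinic visit is rebooked.

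The documents do not say whether withdrawn or lost patients are still sent the postal forms, or how many would return them.

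**The concern.** Both named tests work on an observed change score, so a patient without a 3-month OSS is simply absent. The stated primary analysis is therefore complete-case, although it is labelled intention to treat. Inflating the sample size for attrition protects power. It does nothing about bias if the patients who go missing differ between arms.

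Arm-related loss is plausible here. Both grounds for withdrawal arise after randomisation, and tolerance of the injection could depend on the approach, which is what is randomised. If withdrawn patients leave follow-up, the withdrawal rule and the intention-to-treat statement conflict, and loss could exceed 10%.

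The named tests also use less of the data than the trial collects. Baseline OSS enters only by subtraction, and the 6- and 12-month scores play no part in the 3-month comparison.

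**Working it through.** **Inputs from the documents.** Difference 6, SD of change 9.1, two-sided 0.05, 80% power and 10% attrition (section 7); 43 per arm, 86 in total (sections 3.7 and 7).

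**Assumed, because the documents give no figure.** Correlation r between baseline and 3-month OSS of 0.3 to 0.7; equal SD at each visit; 0% to 100% of patients missing at 3 months returning later forms.

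**1. The plan's own figure.** The two-sample t-test (noncentral t) needs 37.09, so 38 per arm. 38/0.9 = 42.2, rounded up to 43 per arm, or 86. This reproduces the plan exactly.

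**2. Expected loss and power.** 0.10 × 86 = 8.6, about 9 patients. 43 × 0.9 = 38.7 analysed per arm. Power of the t-test at 38.7 per arm is 81.7% (85.6% with all 43).

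**3. Precision.** The standard error (SE) of the test on change is 9.1 × √(2/38.7) = 2.07. With SD σ at each visit, the variance of change is 2σ²(1 − r), and the variance after baseline adjustment is σ²(1 − r²). The ratio of SEs is √[(1 − r²)/(2(1 − r))] = √((1 + r)/2).

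| r | √((1 + r)/2) | SE, adjusted | Reduction |
|---|---|---|---|
| 0.3 | 0.806 | 1.67 | 19% |
| 0.5 | 0.866 | 1.79 | 13% |
| 0.7 | 0.922 | 1.91 | 8% |

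With σ = 9 and r = 0.5 the SD of change is also 9, and the formula gives 2.05 falling to 1.77. Simulated trials under those values, with about 10% missing, gave 2.04 for the t-test on change and 1.76 for the mixed model.

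**4. Patients recovered.** This step uses the expected information for the 3-month contrast in a longitudinal model with baseline, 3, 6 and 12 months, compound symmetry with correlation 0.3 to 0.7, and 4.3 patients per arm missing at 3 months.

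| Missing patients returning both later forms | Effective n per arm |
|---|---|
| None | 38.7 |
| Half | 38.9 to 39.2 |
| All | 39.0 to 39.7 |

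At most about 1 of the 4.3 missing patients per arm is recovered. A patient with only a baseline score adds nothing to the 3-month contrast.

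**5. Bias.** Trials were simulated with no true difference, 43 per arm, SD 9, and correlations 0.5 (baseline, 3 months), 0.45 (baseline, 6 months) and 0.7 (3, 6 months). A missed 3-month score was more likely when 6-month status was poor, with 16% missing in one arm and 5% in the other. Ranges are across separate runs of 4,000 to 20,000 trials with different missingness curves; Monte Carlo error was about 0.03 in a run of 6,000.

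| Missing patients returning the 6-month form | Bias, t-test on change | Bias, mixed model |
|---|---|---|
| All | 0.19 to 0.22 | −0.03 to 0.01 |
| Half | 0.19 to 0.23 | 0.15 to 0.20 |
| None | 0.18 to 0.24 | 0.38 to 0.44 |

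The reversal in the last row can be checked by hand. When loss follows 6-month status and no later form returns, the mixed model reduces to complete-case ANCOVA. Selection shifts the 3-month score in proportion to 0.7 and the baseline score in proportion to 0.45. The change score carries 0.7 − 0.45 = 0.25 of the shift; ANCOVA carries 0.7 − 0.5 × 0.45 = 0.475. The ratio 0.25/0.475 = 0.53 agrees with the biases of 0.22 and 0.41 simulated for those two complete-case analyses (ratio 0.54).

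**The case against.** Several counter-arguments are sound:

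- **Attrition is already in the sample size.** This is true, and planned power holds at the expected loss. It would be wrong to infer that the trial is underpowered because about 9 patients drop out of the test.
- **Intention to treat may mean only analysed as randomised.** That reading is open. The statement is undefined rather than shown to be false. An undefined analysis set alongside a withdrawal rule still leaves the matter to be settled after the data are seen.
- **The bias is small.** Simulated bias of 0.22 points at 16% against 5% missing, or 0.29 at 19% against 5%, is about 4% to 5% of the 6-point difference. Those splits are assumptions, and rebooking of missed visits should limit loss.
- **The proposed model also omits patients with no follow-up OSS.** This stands, which is why the sensitivity analysis is part of the fix.
- **ANCOVA with multiple imputation would also serve.** It would be a reasonable alternative. The mixed model has the convenience of using any returned later score directly.

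A reader might infer that a mixed model would keep most of the missing patients, or would remove the bias. The documents do not support either. The 10% is attrition before the first post-baseline OSS, no later return rate is given, and near-zero bias appears only when every missing patient is assumed to return the 6-month form.

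**Conclusion.** The point holds as a should-change. The stated primary analysis is complete-case, leaves out about 9 of 86 patients at the plan's own attrition rate, and has no missing-data method. The withdrawal rule and the intention-to-treat statement must be reconciled.

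The sure gain from the proposed model is precision through baseline adjustment: an SE about 8% to 19% smaller, assuming a correlation of 0.7 to 0.3 and equal SDs. That gain is separate from retaining missing patients, where recovery is 0 to about 1 effective patient per arm.

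No particular bias is demonstrated in this trial. Its size depends on how loss differs by arm, and any reduction depends on an unknown return rate. With few returns, the model's bias could exceed that of the change-score test.

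**What to change.** Amend section 7 and the matching row of the Study Summary as follows:

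1. **Primary analysis.** A linear mixed model on OSS at 3, 6 and 12 months with arm, time, arm × time, baseline OSS × time and unstructured covariance. Include all randomised patients with any follow-up OSS, in the arm to which they were randomised. The 3-month arm contrast with its 95% CI is the primary result.
2. **Analysis set and withdrawal.** Define the analysis set, reconcile the withdrawal paragraph with the intention-to-treat statement, and state whether withdrawn patients stay in follow-up and in the analysis.
3. **Sensitivity analysis.** Prespecify imputation for patients without follow-up scores, with imputed values shifted away from missing at random over a stated range and with shifts allowed to differ by arm. Report the number missing at each visit by arm.

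The cost is SAP wording and a little more analysis work, with no new data items. The downside is reliance on missing at random. Because few returned forms could make the model more biased than the present test, item 3 should not be treated as optional.

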8.1 Recording of Adverse Events

All Adverse Events (AE) Serious Adverse Events (SAE) will be recorded according to the R&D Office Procedure and the Trust Policy on Incident Reporting.

All adverse events occurring during the study period will be recorded. The clinical course of each event will be followed until resolution, stabilisation, or until it has been determined that the study treatment or participation is not the cause. Serious adverse events that are still on going at the end of the study period will be followed up to determine the final outcome.

No adverse events are anticipated in this study.

9 Data Handling and Record Keeping

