Methodology	
Randomised controlled trial.
 
Patients will attend the orthopaedic clinic and if diagnosed with shoulder subacromial pain syndrome, be offered a steroid injection based on clinical needs. If the patient consents to having a steroid injection, he/she will then be invited to participate in the trial – where they will have an injection by one of the two approaches.
 
Initial clinic assessment: The data collected will include the following,
 
• Which arm is afflicted by the syndrome• Left or right handed (i.e. which is the dominant arm)• Has the patient had previous steroid injection – if so, who by and when• Patient to answer an Oxford Shoulder Score (OSS) questionnaire (The questionnaire used for the study will be in the form of a modified OSS (i.e. In addition to the standard OSS we will inquire about general symptoms and signs (pain, stiffness), duration, hand dominance, previous injuries to the shoulder and previous treatments to the shoulder. (See attached questionnaire)• Patient also asked to complete Disabilities of Arm, Shoulder and Hand (DASH) questionnaire and Short Form 36 Health Survey (SF36) 
At the time of injection:
 
• Assessment of pain prior to injection using a visual analogue scale 0-10 (0=no pain, 10=severe pain)• Assessment of how uncomfortable the injection was using a visual analogue scale 0-10 (0=no discomfort, 10=extremely uncomfortable)• Assessment of pain 20-30mins after injection using a visual analogue scale 0-10 (0=no pain, 10=severe pain)• The injection: Given under sterile aseptic non-touch conditions. This is standard practice and is NOT formally part of the study (i.e. patients would be receiving the injection regardless of whether or not they were participating in the study). Please see below for details. 
Follow up clinic assessment (3 months, 6 months and 1 year post injection):

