1.1 Flowchart of Treatment Schedule

- STEP 1 - New diagnosis of Shoulder Subacromial Pain Syndrome

Patient presents to orthopaedic outpatient clinic and is diagnosed as having shoulder subacromial pain syndrome, offered and agrees to have a steroid injection

- STEP 2 – Does patient meet inclusion criteria?

NO – does not enter study

[figure not shown]
YES – patient initiated to enter study

[figure not shown]
- STEP 3 – Patient consent and study schedule

Patient agrees and consents – patient participates in study. They will be seen in outpatient clinic approximately 3 months following the injection. Postal questionnaires will be sent out at 6 months and 1 year.

Patient does not agree or consent – patient does not enter study

- Please see flow chart below

2 Overview

Patients who present with subacromial pain syndrome (disorders such as subacromial bursitis, rotator cuff tendinopathy, calcific tendinitis, subacromial inflammation with a partial thickness rotator cuff tear) to the orthopaedic outpatient clinic are treated initially with a subacromial steroid injection in addition to physiotherapy for a period of 3 months. This applies to patients who have had no other treatments previously as well as to patients who have had previous physiotherapy or steroid injections prior to presentation. Patients who do not want to undergo the treatment offered are either treated with simple analgesia, sole physiotherapy or surgery.

When a patient with one of the above conditions agrees to go ahead with a steroid injection followed by physiotherapy, the steroid injection is given at the earliest opportunity. The steroid injection is given into the subacromial space either using the anterolateral (front-side) approach (1 cm below and behind the anterior edge of the acromion with the needle aiming towards the under surface of the acromion) or using the posterior (back-side) approach (1cm inferior and medial to the posterolateral acromial edge with the needle pointing towards the anterolateral aspect of the acromion). The exact approach is determined according to the preference of the person carrying out the injection. As a routine we use a 10ml syringe containing 10mls of 0.25% Marcaine along with 40mg triamcinolone with an 18 gauge (green) needle. It is normal for patients to complain of some discomfort during the injection. If a patient experiences any significant discomfort or they

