cannot tolerate the injection for whatever reason, then the injection is discontinued and is not reattempted using a different approach.

Following the injection, patients are questioned on any discomfort experienced during the injection and on whether or not their pain has improved. They are then taken through a protocol of physiotherapy for their shoulder over the subsequent 3 months. A protocol is issued for guidance however therapists are allowed to use other modalities as per their discretion. The frequency of appointments with physiotherapy will depend on patient's symptoms as well as their progression. For study purposes a frequency record of these meetings will be kept and matched to the overall OSS. Patients are seen routinely in 3 months following an injection in order to assess any improvement in symptomatology using the OSS, visual analogue score, DASH and SF36 questionnaires. If the symptoms have improved then no further intervention is taken. Further OSS, visual analogue pain score, DASH and SF36 questionnaires will be posted out at 6 months and 1 year. On the other hand, if they are still troubled with symptoms then the possibility of further injections or surgery is discussed.

The aim of this study is to compare the two approaches that are currently used for subacromial steroid injections, namely the anterolateral and posterior approach, with regards to their effectiveness in improving shoulder symptoms. There will be no deviation from our routine protocol other than randomising patients who agree to participate in this study to either the anterolateral or posterior approach.

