3.4 End of study

Total duration of the study will be 36 months. This includes participant selection, data collection/analysis and publication of findings. For each participant the duration of participation will be 1 year.

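### Section 8.1 commits to recording all adverse events, but no printed form asks about them and no table by approach is planned, so harms other than injection-day pain are likely to be under-recorded

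*Combined protocol and SAP*

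**What the plan says.** Section 8.1 makes an unqualified commitment: "All adverse events occurring during the study period will be recorded". It gives the route: events "will be recorded according to the R&D Office Procedure and the Trust Policy on Incident Reporting". Section 8 adds, on the ground that the medication is given as in normal practice, "therefore standard pharmacovigilance procedures will be used". None of these procedures is reproduced. Section 8.1 ends with "No adverse events are anticipated in this study".

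Section 3.4 sets the length of follow-up: "For each participant the duration of participation will be 1 year". The flowchart in section 1.1 says how the later contacts are made: "Postal questionnaires will be sent out at 6 months and 1 year". Sections 2 and 3.1.2 agree with that. The Methodology row of the Study Summary uses a different label: "Follow up clinic assessment (3 months, 6 months and 1 year post injection".

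Section 2 also provides for injections that are not completed. Where a patient has significant discomfort or "cannot tolerate the injection for whatever reason, then the injection is discontinued", no second attempt is made by the other route. The withdrawal text under section 3.8 takes patients with injection intolerance out of the study.

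**The concern.** A commitment to record every event needs some means of learning that an event has occurred. The forms supplied with the protocol contain no such means, and the later follow-up is planned at a distance. As documented, capture relies on patients raising events themselves, on staff happening to note them, or on procedures the reader cannot see.

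The stated hypothesis is that the two approaches do not differ. If the Oxford Shoulder Scores (OSS) turn out similar, tolerability and harms become a natural basis for comparing the approaches, and the publication plan says the results will be used to influence care. A low event count in the report could then be taken as evidence of safety when it partly reflects not having asked. An injection stopped for intolerance is the event most plausibly linked to the approach. It has no field on the forms, and the patient concerned leaves the study.

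**Working it through.** **1. What each scheduled contact collects.**

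| Contact | Content in the documents | Adverse-event item | Injection-completed item |
|---|---|---|---|
| Injection day (initial questionnaire) | History, pain scale, 12 OSS items; then pain during injection, pain at 20–30 minutes, satisfaction | None | None |
| 3 months, patient part | One pain scale, 12 OSS items | None | Not applicable |
| 3 months, clinician part | Physiotherapy received and management plan | None | Not applicable |
| 6 and 12 months | OSS, pain scale, DASH, SF36 | None listed | Not applicable |

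The numbering of the initial questionnaire runs from 21 to 24, so items may have been lost in reading the file. However, the form announces three post-injection questions and three follow, and the assessment lists in sections 2 and 3.1.2 name no adverse-event item. DASH and SF36 are not printed, so the finding is limited to the forms that are.

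**2. Other places where capture or analysis could be specified.** Section 9.1 does not name adverse events among the details collected. Section 9.2 says only that case report forms apply. Section 3.3 lists no safety endpoint. Its pain endpoints are at 3, 6 and 12 months, so the injection-day scales are not among them. Section 7 plans no comparison or table of events by approach.

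**3. The denominator.** The plan's figure of 43 per arm reproduces. A two-sample t-test with difference 6, SD 9.1, two-sided 0.05 and 80% power needs 37.09, rounded up to 38 per arm; 38/(1 − 0.10) = 42.2, rounded up to 43. This figure serves the OSS endpoint. The documents give no adverse-event rate.

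**4. What zero events in one arm would show.**
- Complete capture: upper limit = 1 − 0.05^(1/43) = 0.0673, or 6.7% (one-sided 95%).
- If a fraction *a* of events is captured, the limit applies to the recorded rate, so the true rate could be as high as 0.0673/*a*.
- *a* = 0.5: 0.0673/0.5 = 0.135, about 13%.
- *a* = 0.25: 0.0673/0.25 = 0.269, about 27%.

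**5. Chance of seeing at least one event in a 43-patient arm**, 1 − (1 − *p·a*)^43, for assumed true rates *p*:

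| True rate | All captured | Half | Quarter |
|---|---|---|---|
| 1% | 35% | 19% | 10% |
| 2% | 58% | 35% | 19% |
| 5% | 89% | 66% | 42% |
| 10% | 99% | 89% | 66% |

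**6. Comparing arms.** For assumed true rates of 5% and 20%, approximate power with 43 per arm is 56% with full capture, 30% with half and 17% with a quarter.

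**The case against.** A reader might infer that harms by approach will be missed, or that the design cannot deliver what section 8.1 promises. The documents do not support that. Section 8.1 names an R&D procedure and a Trust policy. Since neither is reproduced, they may contain an adverse-event form or active questioning. Adverse events need not be recorded on a patient questionnaire at all.

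Nor is capture left wholly to patients volunteering events. Staff see them at 20–30 minutes and before they leave hospital, physiotherapists see them over the next 3 months, and there is a clinic visit with examination at 3 months. Patients still troubled then discuss further treatment, and GPs are told of participation. Tolerability is also measured in part: pain during injection, pain afterwards and satisfaction are collected in both arms. Stopped injections should surface as withdrawals.

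It would also be too strong to call the last sentence of section 8.1 a flat contradiction of section 2. A rule for what happens if an injection is not tolerated is a contingency, and section 2 treats some discomfort as normal. The wording needs reconciling, no more.

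Finally, the capture fractions have no source in the documents. Even full capture gives only about 56% power for a 5% versus 20% comparison, so event counts alone are unlikely to settle the choice of approach.

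All of this stands. What remains is that no contact has a specified, standard question about harms, no field records whether the injection was completed, and no table by approach is planned. A policy on where to record known events does not show that participants will be asked.

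**Conclusion.** The concern holds as one of likely under-recording. Section 8.1 commits to complete recording, while the documents show passive capture on the printed forms, weakest after 3 months. A zero count could not be read as no harm: 0/43 excludes true rates above 6.7% only if capture is complete, and is compatible with rates up to about 13% or 27% at half or quarter capture.

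This rests on three things: the two capture fractions, which are assumptions; all 43 patients per arm being followed; and the unseen R&D and Trust procedures not already supplying active questioning. Reading the study period as one year per participant is reasonable given section 3.4, though section 8.1 does not say so. The primary OSS result and the sample size are unaffected. The change should be made because it is cheap and bears on how the safety statement in the report can be read.

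**What to change.** - **Injection-day form:** add whether the injection was completed as allocated (yes/no), the reason if it was stopped, and any immediate event.
- **3-, 6- and 12-month forms:** add one yes/no question with free text on new problems, or GP or hospital attendance, since the last form.
- **Section 7:** add a table of stopped injections and adverse events by allocated approach, counting patients withdrawn for intolerance.
- **Section 8.1:** reconcile the statement that no events are anticipated with the provision for stopped injections in section 2 and the withdrawal text under section 3.8. Reconcile that withdrawal text in turn with the intention-to-treat statement in section 7.
- **Study Summary:** reconcile the clinic-assessment heading for 6 and 12 months with the postal follow-up described elsewhere.

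The cost is a few lines on existing forms, one table, and more reports to review. Sample size, treatment and visits do not change.
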